Levetiracetam Versus Valproate in Idiopathic Generalized Tonic-clonic Seizures

ID: NCT03940326

8.11.2020

Study protocol

This study was a non-randomized open label active-controlled clinical trial with a two-parallel-group design aimed to compare efficacy of levetiracetam (LEV) with valproate (VPA) for treatment of patients with idiopathic (genetic) generalized epilepsy. Patients aged ≥ 16 years with diagnosis of genetic generalized tonic-clonic seizures only (GTCS) or juvenile myoclonic epilepsy (JME) who were referred to our tertiary University hospital and epilepsy clinic were included. Normal brain magnetic resonance imaging (MRI), lack of focal epileptic discharges with or without generalized epileptiform discharges in electroencephalography (EEG) and seizure symptomatology in favor of GTCS or JME were mandatory. Patients with history of hepatic, renal and hematologic disorders, known psychosis, psychogenic non-epileptic seizure, status epilepticus and illegal drug abuse, patients who had been treated with LEV or VPA in the last 6 months and those with poor adherence to medications or plan for pregnancy were excluded. The study was approved by University ethics committee and performed in accordance with the International Conference on Harmonization Good Clinical Practice guidelines and the Declaration of Helsinki. All patients provided written informed consent before participation.

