Patients were treated by LEV or VPA. LEV was started with 500 mg/day (twice daily as equal doses) and the dose was increases by 500 mg/week to a total dose of 2000 mg/day if needed. Starting dose for VPA was 500 mg/day with 500 mg/week increase to the maximum dose of 1500 mg/day in two divided doses based on clinician's decision. Patients, who experienced adverse events (AEs) during titration which could be ameliorated by dose reduction, were reverted to previous acceptable dose. If one episode of seizure occurred, doses were increased to maximum 3000 mg/ day for LEV and 2000 mg/day for VPA with the same titration protocol, according to clinician's judgment. Evaluations have scheduled at weeks 4, 12 and 26 after initiation of treatment. In each visit by neurologist, adherence to AED, seizure recurrence and AEs were assessed. The primary outcomes were time to first seizure and seizure freedom rate at 6 months after start of treatment. The secondary outcomes were defined as time to withdrawal and withdrawal rate at 6th month and also severity of adverse events. Withdrawal rate was calculated based on discontinuation of monotherapy with each medication due to AEs, lack of efficacy and need to drug switch or combination therapy.

Statistical analysis

SPSS version 19 software (SPSS Inc.) was used for statistical analysis. Chi-square test or Fisher's exact test were used to compare categorical variables between groups. Numerical variables were analyzed with student's t-test or Mann-Whitney test, according to distribution. Time to first seizure and time to withdrawal were analyzed using the Kaplan–Meier survival curves. For analysis of time to first seizure, patients who did not experience any seizure during the first 26 weeks of treatment were censored at the end of 26 weeks. For analysis of time to withdrawal, patients who discontinue medication before 26 weeks were considered to have the event. Cox's regression model was used to investigate time to withdrawal and time to first seizure. A Hazard ratio (HR) of less than 1 was considered in favor of LEV. P-value of less than 0.05 was considered statistically significant.

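### The primary event is a first seizure of unspecified type in a mixed GTCS-only and JME population, so the pooled hazard ratio need not describe the tonic-clonic control named in the title

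*Combined protocol and SAP*

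**What the plan says.** The title is "Levetiracetam Versus Valproate in Idiopathic Generalized Tonic-clonic Seizures". The Study protocol section states a wider aim: to compare the two drugs "for treatment of patients with idiopathic (genetic) generalized epilepsy". Eligibility matches that aim and requires a "diagnosis of genetic generalized tonic-clonic seizures only (GTCS) or juvenile myoclonic epilepsy (JME").

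On outcomes, the same section says: "The primary outcomes were time to first seizure and seizure freedom rate at 6 months after start of treatment". No seizure type is named. The Statistical analysis section defines the event only indirectly, through its censoring rule: "patients who did not experience any seizure during the first 26 weeks of treatment were censored at the end of 26 weeks". The document does not say whether a myoclonic jerk is a seizure for this purpose.

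On data collection: "Evaluations have scheduled at weeks 4, 12 and 26 after initiation of treatment", and "In each visit by neurologist, adherence to AED, seizure recurrence and AEs were assessed". Recording by seizure type is not mentioned. A seizure does not take the patient out of the study: "If one episode of seizure occurred, doses were increased to maximum 3000 mg/ day for LEV and 2000 mg/day for VPA".

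The trial is open label and non-randomized. The Cox model is stated without covariates or strata, and no result by syndrome or by seizure type is planned.

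**The concern.** GTCS-only patients have, by diagnosis, tonic-clonic seizures only. JME is named for its myoclonic seizures. If every seizure type counts, one primary outcome measures different things in the two syndromes, and a JME patient's first jerk fixes both primary outcomes whatever happens later to tonic-clonic control.

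Two things are at stake. First, if the drugs act differently on jerks and on tonic-clonic seizures, the pooled hazard ratio describes neither, even when the arms have the same syndrome mix. Second, allocation is not randomized, so the mix may differ between arms. With no syndrome term in the model, that difference can pass for a drug effect. A reader who takes the title at face value would read the result as tonic-clonic control.

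**Working it through.** The document gives no sample size, event count, power, JME share or risk by seizure type. There is no planned figure to reproduce, so the check is a reading of the text followed by an illustration on assumed inputs.

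**Text.**
- GTCS-only patient: first seizure means first tonic-clonic seizure.
- JME patient, literal reading: the event is whichever comes first, a jerk or a tonic-clonic seizure. Time at risk for time to first seizure then ends and seizure freedom is lost. Visits and the withdrawal analysis still run to week 26.
- JME patient, if jerks were not meant to count: the two syndromes share one event, but the plan does not say so. Each neurologist then decides, unblinded, at weeks 4, 12 and 26.

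**Illustration (every input assumed).** Hazards are constant over 26 weeks. Tonic-clonic seizures can occur in all patients, with 26-week risk 25%. Jerks occur in JME only, with 26-week risk p = 20%, 40% or 60%. The JME share is s.

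- Cumulative hazards on valproate (VPA): Hg = −ln(1 − 0.25) = 0.288; Hm = −ln(1 − p). For levetiracetam (LEV), each is multiplied by the assumed drug effect on that seizure type.
- Free of any seizure at week 26: S = (1 − s)·exp(−Hg) + s·exp(−Hg − Hm).
- Apparent HR = ln S(LEV) / ln S(VPA). This is a ratio of cumulative hazards at week 26, an approximation to the Cox estimate. Below 1 favours LEV, as in the plan.

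*A. Same JME share in both arms, true tonic-clonic HR 1.00.* Example with s = 0.5, p = 0.4, myoclonic HR 2.0:
- VPA: S = 0.75 × (0.5 + 0.5 × 0.6) = 0.600
- LEV: S = 0.75 × (0.5 + 0.5 × 0.6²) = 0.510
- HR = ln 0.510 / ln 0.600 = 1.32

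*B. No drug effect on either type, JME shares differ.* Example with 20% JME on LEV, 50% on VPA, p = 0.6:
- LEV: S = 0.75 × (0.8 + 0.2 × 0.4) = 0.660
- VPA: S = 0.75 × (0.5 + 0.5 × 0.4) = 0.525
- HR = ln 0.660 / ln 0.525 = 0.64

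*C. Same JME share, true tonic-clonic HR 0.67.* Same formulas, with myoclonic HR 1.0 or 1.5.

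| Case | Varied (with p = 20%, 40%, 60%) | True tonic-clonic HR | Apparent HR |
|---|---|---|---|
| A | s = 20%, 35%, 50%; myoclonic HR 0.67, 1.5, 2.0 | 1.00 | 0.85 to 1.32 |
| B | LEV 20% vs VPA 40% | 1.00 | 0.89 to 0.74 |
| B | LEV 30% vs VPA 50% | 1.00 | 0.89 to 0.75 |
| B | LEV 20% vs VPA 50% | 1.00 | 0.84 to 0.64 |
| B | LEV 50% vs VPA 30% | 1.00 | 1.12 to 1.33 |
| C | s = 20%, 35%, 50%; myoclonic HR 1.0, 1.5 | 0.67 | 0.71 to 1.02 |

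If only tonic-clonic seizures count and the drugs do not differ on them, both arms have 25% events and HR = 1.00 whatever the JME share.

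**What each remedy reaches.** In B the drug effect within each syndrome is null, so stratifying or adjusting for syndrome removes the distortion. In A it does not remove it inside JME: with p = 0.4 (Hm = 0.511) and myoclonic HR 2.0, the JME stratum alone gives (0.288 + 2 × 0.511) / (0.288 + 0.511) = 1.310 / 0.799 = 1.64 against a tonic-clonic HR of 1.00. Seizure type is needed for that.

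**The case against.** The strongest reply is that the title is the outlier. The stated aim is generalized epilepsy and JME is deliberately enrolled, so a first seizure of any kind is a fitting primary event. Ignoring later seizures is also inherent in any time-to-first-event outcome, and poor later control can still show up as withdrawal for lack of efficacy. This stands. It is the reason to keep the any-seizure outcome as primary. It does not supply a definition of the event or an analysis by syndrome.

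Several stronger readings are tempting, and the document does not support them:
- A reader might infer that a jerk ends follow-up. It ends time at risk for one outcome and settles the other; dose increases, visits and the withdrawal analysis continue.
- A reader might take it as settled that jerks are events. That is the literal sense of a censoring sentence, not a stated rule, and clinicians may have counted only tonic-clonic seizures. What the text shows is an undefined event.
- A reader might infer that the pooled estimate can never be separated. Syndrome is the entry diagnosis, so a split by syndrome remains possible though unplanned. Only a split by seizure type depends on records that the plan does not require.
- A reader might infer that tonic-clonic seizures should become the primary event. The aim does not call for that, and the document is written in the past tense, so such a switch now could be a post hoc change of endpoint.

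**Conclusion.** The point holds as a gap in definition and reporting. The title is narrower than the aim and population, the primary event has no stated seizure type, and no tonic-clonic or syndrome-specific result is planned. Following the plan as written yields one hazard ratio that need not describe tonic-clonic control or either syndrome.

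Its size cannot be obtained from the document. The ranges above show only that the any-seizure hazard ratio can depart from the tonic-clonic one in either direction, including losing a true tonic-clonic HR of 0.67 (apparent value up to 1.02). They rest on the assumed risks, JME shares and drug effects, on constant hazards, and on jerks being counted. If jerks were not counted, the mixing of event types disappears and the remaining faults are the missing definition, the missing syndrome term and the title. This is an inexpensive improvement to make, not evidence that the trial's result is biased.

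**What to change.** 1. Keep the any-seizure outcome as primary, in line with the stated aim, and state which seizure types count, including whether myoclonic jerks do.
2. Record the type of each seizure at the existing visits, or retrieve it from clinical notes if visits are complete.
3. Report time to first tonic-clonic seizure and tonic-clonic freedom at 26 weeks beside the any-seizure results, labelled as supplementary if they are added after data collection.
4. Give the drug effect separately for GTCS-only and JME with a drug-by-syndrome estimate and confidence interval, and stratify or adjust the Cox model for syndrome, which is known at entry.
5. Align the title and conclusion with any seizure in a mixed GTCS-only and JME population.

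Cost: one field at existing visits, or a search of the notes, and a few tables. The tonic-clonic and by-syndrome estimates will rest on fewer events and have wider confidence intervals. If seizure type was never captured, item 3 is lost, but items 4 and 5 still apply, and item 1 reduces to reporting how jerks were handled in practice.
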